Study Design	Randomized, double-blind, placebo-controlled parallel trial of 20 subjects with HPS. Eligible subjects will be randomly assigned 1:1 to receive either letrozole 2.5 mg orally daily or placebo for 6 months.
Number of Subjects	20 total subjects; 10 subjects at each site
Duration of Administration	6 months
Reference therapy	There is no reference therapy

Statistical Methodology	
Primary endpoint:
 
 • Difference in changes in AaPO₂ between letrozole and placebo groups at 6 months. 
Secondary endpoints:
 
 • Difference in changes in intrapulmonary shunting between letrozole and placebo groups at 6 months • Difference in changes in estradiol, progesterone, testosterone levels between letrozole and placebo groups at 3 months and 6 months • Difference in changes in SF36 scores and mMRC dyspnea scale scores between letrozole and placebo groups at 6 months • Difference in changes in distance walked in six minutes between letrozole and placebo groups at 6 months • Difference in changes in PaO₂ and oxygen saturation by pulse oximetry between letrozole and placebo groups at 3 months and 6 months • To assess the effect of letrozole versus placebo on AaPO₂ at 3 months and 6 months • Safety and side effects associated with letrozole administration in patients with HPS 
Sample size and power:
 
A total of 20 patients will be enrolled (10 letrozole, 10 placebo), which will provide 80% power to detect a 13.2 mm Hg difference in changes in AaPO₂ ($\alpha = 0.05$).
 
Data analysis:
 
The primary analysis will compare the absolute change from baseline to 6 months in AaPO₂ between the blinded treatment arms using a two-sample t-test. Incidence of adverse events and secondary endpoints will also be analyzed.

-------------------------	---

1 Introduction

This document is a protocol for a human research study. This study will be carried out in accordance with the applicable United States government regulations as well as research policies and procedures of both Mayo Clinic and the University of California, San Francisco.

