8.2 Sample Size, Effect Size, and Power Calculations

Our primary endpoint is change in A-a gradient over 6 months between the treatment and placebo groups. We expect 20 patients to enroll in this study. We have set $\alpha = 0.05$ and the standard deviation of change in AaPO₂ at ~ 10 mmHg. Assuming all this, we will have an 80% power to detect a 13.2 mmHg change in A-a gradient.

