8.4 Statistical Methods

8.4.1 Data Analysis

The intent-to-treat analysis will include all randomized subjects. Hypothesis testing will use two-sided α level 0.05 without correction for multiplicity. We will summarize demographics and baseline and follow-up endpoints.

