8.4.3 Analysis of Treatment Assignment and Outcome Measures

The primary analysis will compare the absolute change from baseline to 6 months in AaPO2 between the blinded treatment arms using a two-sample t-test. This will be supplemented with mixed analysis of variance methods to allow inclusion of the baseline value (fixed) and clinical site (random). If the data are not normally distributed, they will be transformed. For dichotomous outcomes, logistic regression will be used. For secondary outcomes with additional longitudinal assessments, including results of the plasma biomarker assessments, 6MWT, SF-36, ABG, and the modified Medical Research Council Dyspnea Scale, linear mixed effects models or generalized estimating equations will be used as appropriate. All patients will be assessed for toxicity and included in the safety analysis. This analysis will include summaries of the incidence and grade of toxicities. Patients will be evaluated for serious adverse events. Safety interim analyses will be performed and reported at each continuing review with the IRB.

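### The open-ended rule to transform non-normal data should not apply to the primary endpoint: it can move the result off the mmHg scale after the data are seen, and the t-test does not need it

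*Combined protocol and SAP*

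**What the plan says.** Section 8.4.3 defines the primary variable as the "absolute change from baseline to 6 months in AaPO2", compared between arms by a two-sample t-test and supplemented by a mixed analysis of variance with baseline (fixed) and site (random). The next sentence reads: "If the data are not normally distributed, they will be transformed". The same paragraph goes on to dichotomous and longitudinal secondary outcomes.

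The plan does not say whether "the data" are raw AaPO₂ values, change scores or model residuals. It names no normality check, threshold or transformation, no way of reporting a transformed result in mmHg, and no rank-based or permutation alternative. Nothing restricts the rule to secondary outcomes.

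The design target is in mmHg. Section 8.2 claims "80% power to detect a 13.2 mmHg change in A-a gradient", with the "standard deviation of change in AaPO₂ at ~ 10 mmHg". Section 8.4.1 sets the test level: "Hypothesis testing will use two-sided α level 0.05 without correction for multiplicity". Section 5.7 lists the statistical analyst among those who are unmasked, although Section 8.4.3 speaks of comparing blinded arms.

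**The concern.** The primary result should be fixed before the data are seen, on the scale on which the trial was designed. This rule leaves three things open.

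- **Choice.** Someone must judge normality from 10 values per arm and then pick a transformation. The plan does not ensure that this is done blind to treatment.
- **Feasibility.** The transformations most analysts would try need positive (or non-negative) values, and a change score takes both signs.
- **Scale.** A difference in mean cube root, or in mean log, is not a difference in mmHg and cannot be set against 13.2 mmHg.

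At stake are the interpretability of the primary estimate and, in a minority of trials, the side of 0.05 on which the result falls.

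**Working it through.** **1. The plan's own figure.** Inputs: difference 13.2 mmHg and SD 10 (Section 8.2), 10 per arm (Study Summary), two-sided α 0.05 (Section 8.4.1).

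d = 13.2/10 = 1.32; noncentrality = d√(n/2) = 1.32 × √5 = 2.95 on 18 df. The noncentral t gives power 79.7% and a minimum detectable difference of 13.25 mmHg. The stated 80% is reproduced as a two-sided t-test on untransformed mmHg change. The normal approximation gives 83.9% and a one-sided t-test 88.4%, so neither is the source.

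**2. Negative change scores.** P(change < 0) = Φ(−μ/10), and P(at least one among n) = 1 − (1 − p)ⁿ. The means are assumptions; the SD is the plan's.

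| Mean change μ | Share negative | At least one negative |
|---|---|---|
| 0 | 50% | 99.9% of 10 |
| +5 | 30.9% | 1 − 0.691²⁰ = 99.9% of 20 |
| −13.2 | 90.7% | above 99.9% of 10 |
| +13.2 | 9.3% | 62% of 10 |

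Even in the last row, adding a second arm of 10 with mean 0 gives 1 − 0.907¹⁰ × 0.5¹⁰ = 99.96% for the trial. In a simulated set of 20 changes, log and square root were undefined for 13 values and Box-Cox refused to run. Cube root and Yeo-Johnson ran on all 20.

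**3. How well could a check trigger the rule?** The plan names none. Assume Shapiro-Wilk at 0.05 (10,000 runs per shape; shapes are assumptions).

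| True shape | Flagged, n = 10 | Flagged, 20 pooled residuals | Type I error, untransformed t-test |
|---|---|---|---|
| Normal | 4.7% | 4.7% | 4.6% |
| t, 5 df | 11% | 16% | 4.3% |
| t, 3 df | 19% | 31% | 4.3% |
| Gamma, skewness 1 | 14% | 24% | 4.9% |
| Lognormal, σ 0.5 | 25% | 44% | 4.7% |
| Exponential | 43% | 70% | 4.7% |
| Lognormal, σ 1 | 61% | 85% | 3.3% |

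If either arm alone can trigger the rule, normal data are flagged in 9.9% of trials. The last column takes the same shape in both arms. A short-tailed uniform shape gave 5.4%.

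**4. Scale.** If raw AaPO₂ were logged before forming the change, a 13.2 mmHg fall is a ratio of (b − 13.2)/b: 0.34 from a baseline b of 20 mmHg, 0.67 from 40 and 0.78 from 60 (baselines assumed). No single transformed effect corresponds to 13.2 mmHg.

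**5. What the open choice does to the test.** These are simulations at 10 per arm; the transformations are assumptions.

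- One fixed transformation (Yeo-Johnson) after a failed check: type I error about 5%.
- Free choice of the smallest p-value: about 6–7% with a short list, and 7–9% when raw, cube-root, Yeo-Johnson, two shifted-log and normal-score versions are all tried.
- The long list, opened only after a failed check in either arm: 5.0–6.7%.
- True effect 9 mmHg, normal data: raw and cube-root t-tests disagree on significance in 13% of trials.

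**The case against.** The strongest reply is that little harm follows. A disciplined analyst with one transformation and one check keeps type I error near 5%. The check would seldom fire on mildly non-normal data, so the result would usually stay in mmHg. The two-sample t-test remains the named test; only its scale could change. Sections 8.4.1 and 8.4.2 plan descriptive summaries that should be available in mmHg in any case. For hormone levels, which are positive, transformation is ordinary practice. All of this stands, and it keeps the point modest.

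Two stronger readings are tempting, and the documents do not support them.

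- **A reader might infer that the rule cannot be applied at all.** It can. Cube root, Yeo-Johnson, shifted log and rank-based scores accept negatives. Raw AaPO₂, positive at entry under Section 4.1, could be logged before the change is formed.
- **A reader might infer that the plan relies on an uninformative normality test.** The plan names no test. The one assumed here is weak for moderate departures but flags gross skew in 70–85% of runs on 20 residuals.

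What the reply does not answer is that the plan fixes none of these choices. The harmless case depends on discipline that is not written down, while the analyst is unmasked.

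**Conclusion.** The point holds in a limited form. The rule is data-driven, reaches the primary endpoint, and leaves the transformation open to an unmasked analyst. The usual transformations are undefined for the primary variable, and every nonlinear one breaks the link to the mmHg target.

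The size is moderate. Type I error ranges from about 5% to 9% depending on how freely the choice is made, and the conclusion could flip in roughly one trial in eight (13%) for a true 9 mmHg effect. In return the rule buys the primary test little, since type I error without it was 3.3–4.9% for the normal, skewed and heavy-tailed shapes simulated.

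These figures rest on the plan's SD of 10 mmHg, all 10 patients per arm contributing, the same distributional shape in both arms, and assumed shapes, checks and transformations. The completers analysis in Section 8.4.5 could leave fewer than 10 per arm. It should not be inferred that the sample size is wrong: the 80% power is correct for the untransformed t-test.

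**What to change.** In Section 8.4.3:

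1. State that the transformation rule does not apply to the primary endpoint, and that the comparison of change in mmHg stays primary whatever the distribution.
2. Pre-specify one sensitivity analysis that needs no normality: either a permutation test of the mean difference, or a Wilcoxon test with a Hodges-Lehmann interval in mmHg. Name which.
3. Keep the rule, if wanted, for positive-valued secondary outcomes such as hormone levels.

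Naming the variable, trigger and transformation, and requiring an mmHg estimate alongside, would also close the gap. Exempting the primary endpoint is simpler and keeps the result on the scale of the power statement.

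The cost is a change of wording and one extra analysis, with possibly a little lost power under strong skew. No patient, visit or sample-size change is needed.

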8.4.4 Survival Analysis

A log-rank statistic will be used to compare time to death, although there are expected to be few events.

8.4.5 Missing Data and Dropouts

We will attempt to minimize missing data; however we have planned for its occurrence. For subjects lost to follow-up, we will use all of the information available until the end of follow-up. This protocol will continue to be followed and test procedures performed as prescribed even if a subject drops out of the therapeutic portion of the study. That is, if a subject decides that he/she does not wish to continue taking the study drug, the subject will stop the investigational treatment, but will still be strongly encouraged to continue to follow up with the study personnel for all scheduled study procedures (e.g., phlebotomy, echocardiography), so that missing data (and assumptions regarding these data) will be minimized.

For the primary end point, we will perform an analysis of completers only. We will also perform additional sensitivity analyses using imputation to assess the impact of missing data for the primary and secondary end points.

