4.6 Early Withdrawal of Subjects

4.6.1 When and How to Withdraw Subjects

A subject may be withdrawn from the study prior to that subject completing all of the study related procedures for the following reasons.

- Unanticipated adverse effects that are possibly or probably related to the study drug
- patients who miss more than 20% of doses or are not adherent to protocol requirements.
- Disease progression
- Subject decision to withdraw from the study (withdrawal of consent)
- Liver transplantation

Subjects who withdraw from the study for safety concerns or disease progression will be included in the primary analysis (safety and tolerability). As this is a short-term study, there will be no specific clinical follow-up for subjects withdrawn from the study.

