8.3 Disposition of Subjects and Baseline Comparisons

Summaries of all subjects screened, recruited, randomized, and the number who complete visits at 3 and 6 months post-randomization will be provided, according to the CONSORT guidelines. The treatment groups will be compared at baseline with respect to demographics and baseline measurements related to efficacy and safety without formal statistical testing.

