8.6 Protocol Violations

Serious protocol violations such as discontinuation of experimental treatment unrelated to adverse events (AEs) will be carefully recorded and regularly reviewed by the Principal Investigator. Remedial changes in procedure will be recommended where feasible to reduce the incidence of such violations. The causes and circumstances of all violations will be documented

where known for purposes of future secondary analyses and interpretation. Because all primary analyses will be intent-to-treat, it is essential that violations be kept to a minimum, especially where it is possible to influence their rate of occurrence.

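### Section 8.4.5 analyses the primary AaPO₂ end point in undefined completers, while 8.4.1 and 8.6 promise intent-to-treat: the primary population and the handling of missing month-6 values must be stated

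*Combined protocol and SAP*

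**What the plan says.** Section 8.4.3 makes the primary analysis a two-sample t-test on change in AaPO₂ from baseline to month 6. It names no analysis set and no rule for missing values.

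Three other places bear on who is analysed:

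- Section 8.4.5: "For the primary end point, we will perform an analysis of completers only". Imputation follows as additional sensitivity work, with no method named.
- Section 8.4.1: "The intent-to-treat analysis will include all randomized subjects".
- Section 8.6: "Because all primary analyses will be intent-to-treat, it is essential that violations be kept to a minimum".

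No section defines a completer. The nearest wording is in section 8.3, on disposition only: "the number who complete visits at 3 and 6 months post-randomization will be provided".

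On follow-up, section 8.4.5 says patients who stop study drug "will still be strongly encouraged to continue to follow up with the study personnel for all scheduled study procedures", and section 9.4 asks for the same in order to protect the intention-to-treat analysis. For patients who are lost, section 8.4.5 adds: "For subjects lost to follow-up, we will use all of the information available until the end of follow-up". Section 4.6.1, on withdrawal from the study, says "there will be no specific clinical follow-up for subjects withdrawn from the study". Section 4.6.2 says it may still be important to collect some follow-up data on such patients. Section 5.5 asks patients who miss more than 20% of doses to withdraw from the study.

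**The concern.** Section 8.4.5 gives one rule aimed specifically at the primary end point, and that rule does not describe the population in sections 8.4.1 and 8.6. What follows depends on a word the plan leaves undefined.

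If it means finishing study drug, two analysts following the plan could report different primary results from the same data. One of those results would depend on who left after randomisation. The reasons for leaving listed in section 4.6.1 include adverse effects, disease progression and poor adherence, any of which can be related to treatment or to outcome. If it means having a month-6 value, the two analysts agree, but the plan leaves open how the other randomised patients enter an analysis of everyone randomised.

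With 10 patients per arm, one or two exclusions can move the result. Section 5.7 also unmasks the statistical analyst, so the choice should not still be open when outcome data are seen.

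**Working it through.** **Inputs.** From the Study Summary and sections 8.2 and 8.4.1: 10 patients per arm, SD of change about 10 mmHg, two-sided α 0.05, 80% power for 13.2 mmHg. The documents give no dropout rate or mechanism, so every exit scenario below is an assumption.

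**The plan's own figure.** SE of the difference = 10 × √(1/10 + 1/10) = 4.47 mmHg. Noncentrality = 13.2 / 4.47 = 2.95 on 18 df. Two-sided t-test power = 79.7%, which matches the stated 80%. It requires all 20 patients to have an analysed month-6 value.

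**What each meaning of completer does.**

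| Meaning | Effect on the section 8.4.3 t-test | What is lost |
|---|---|---|
| Has a month-6 blood gas | None: a month-6 change exists only for these patients | Month-3 AaPO₂ of patients without month 6 |
| Finished study drug | Off-drug patients who attended month 6 are dropped | Their month-6 AaPO₂; the comparison depends on exit |
| Either, but only as a supplement to intent-to-treat | None on the primary result | The primary rule for missing values is then unstated |

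**Size under the second meaning.** Simulated with change ~ N(0, 10), 10 per arm, no true effect and 400,000 trials per scenario. The k patients in one arm with the highest exit score are removed, where the score has correlation ρ with the change (leavers tend to be those whose gradient rose most). The t-test is then applied.

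| ρ | Shift in difference, k = 1, 2, 3 (mmHg) | False-positive rate, k = 1, 2, 3 |
|---|---|---|
| 0 | 0, 0, 0 | 5.0%, 5.0%, 5.0% |
| 0.25 | −0.4, −0.8, −1.1 | 5.2%, 5.3%, 5.6% |
| 0.5 | −0.9, −1.6, −2.3 | 5.6%, 6.5%, 7.6% |
| 1.0 (bound) | −1.7, −3.2, −4.6 | 7.4%, 11.6%, 16.9% |

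If 1, 2 or 3 are removed from both arms, the mean does not shift. The rates are 5.1–5.2% at ρ = 0.25, 5.4–5.7% at ρ = 0.5, and 7.4%, 9.1% and about 10.5% at the bound. Removing extremes shrinks the SD, so part of the one-arm inflation is SD shrinkage and not shift.

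**What month 3 can recover when month 6 is absent.** Simulated with 200,000 trials; leavers have a month-3 change with correlation r to the month-6 change, and a regression estimate is used with the slope pooled over arms. At the ρ = 1 bound, the shift remaining for k = 1, 2, 3 is −1.6, −2.9, −4.2 mmHg at r = 0.3; −1.3, −2.5, −3.6 at r = 0.5; and −0.9, −1.7, −2.6 at r = 0.7. If exit depends only on the month-3 value (r = 0.5), the shift goes from −0.9, −1.6, −2.3 to about zero. Month 3 therefore helps, but does not remove bias from exit that depends on the month-6 outcome.

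**Cost of keeping off-drug values.** Assume k of 10 letrozole patients stop drug and have no effect at month 6. The mean difference is 13.2 × (1 − k/10) = 11.9, 10.6, 9.2 mmHg for k = 1, 2, 3, and power is 71%, 61%, 50%. Dropping the same patients, with effect and SD unchanged, gives 77.3% (10 v 9), 74.3% (10 v 8) and 70.7% (10 v 7). The choice of population changes both the question and the power.

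**The case against.** The strongest reply is that section 8.4.5 never calls the completer analysis primary. It announces an analysis in completers and then further sensitivity analyses, so completers may have been meant to sit beside intent-to-treat. That stands as a possible reading, and a reader who infers a certain contradiction goes further than the text allows. But nothing says it is a supplement. It is the only missing-data rule given specifically for the primary end point, and imputation is described as additional to it.

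A reader might also infer that the plan intends to discard off-drug month-6 values. Context points the other way. The sentence follows a paragraph that keeps these patients in follow-up to limit missing data, and section 9.4 gives intention-to-treat as the reason. Having a month-6 value is the more natural meaning. The damaging one is possible because the term is undefined, but it is the weaker reading.

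Nor does the plan ignore month-3 values altogether. AaPO₂ at 3 and 6 months is a secondary end point, and section 8.4.3 plans mixed models or GEE for longitudinal blood gases. A mixed model would use month 3 from patients without month 6. It is a secondary analysis, though. The mixed analysis of variance that supplements the primary t-test adds baseline and site, not month 3.

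Finally, withdrawal from the study (4.6.1) and stopping drug (8.4.5, 9.4) are different states, so the follow-up sections are not in flat opposition. They still leave unclear which patients will have a month-6 value, for example those asked to withdraw under section 5.5.

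**Conclusion.** The concern holds as an unreconciled and undefined primary population that should be fixed. It is not a demonstrated bias. Sections 8.4.5, 8.4.1 and 8.6 do not together say who is in the primary AaPO₂ analysis or how a missing month-6 value is handled.

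The numerical effect ranges from none (completer means a month-6 value exists, or the analysis is a supplement) to material (completer means finished drug, and exit is strongly tied to outcome). For 1 to 3 exclusions from one arm, the false-positive rate runs from 5% through 5.2–5.6% and 5.6–7.6% to a bound of 7–17%. The 17% should not be read as an expected error rate: it needs exactly the three patients with the largest rise to leave, all from one arm. All of these figures assume normal changes with SD 10, no true effect and an exit pattern that the documents do not supply.

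**What to change.** 1. In sections 8.4.3, 8.4.5 and 8.6, state one primary population: all randomised patients in their assigned arm, including AaPO₂ collected after stopping study drug.
2. Define completer, and label that analysis a sensitivity analysis.
3. For patients with no month-6 value, name one method that uses the scheduled month-3 AaPO₂. Either make the mixed model already planned for blood gases, with baseline AaPO₂, the primary handling, or use multiple imputation followed by the planned t-test. State the missing-at-random assumption. A simple missing-not-at-random check is optional, but would be informative because month 3 does not remove outcome-dependent bias.
4. Reconcile sections 4.6.1, 4.6.2, 5.5, 8.4.5 and 9.4 on whether assessments continue after withdrawal.
5. Fix these choices before anyone sees unmasked outcome data.

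The cost is wording and a little analysis work. No visits or tests are added, since the month-3 and month-6 blood gases are already scheduled. The real price is the dilution shown above if the effect is lost off drug. That is the accepted cost of the intent-to-treat question the protocol says it is asking.
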